5.1. PARTICIPANT DISPOSITION, DEMOGRAPHIC AND BASELINE CHARACTERISTICS

Participant disposition will be presented for the screening analysis set. A summary table will be generated for the overall population. The number of participants who were screened, screen failures, and the reason for screen failure will be summarized. Additionally, the number of participants in each analysis population will be summarized. The end of treatment and reason for treatment discontinuation for each drug in the treatment combination (ie, lerapolturev and anti-PD-1) will be provided; the end of study status and reason the participant discontinuation from study will also be provided. The survival status and primary reason for death will be presented. Additionally, the number of days on treatment and number of days on study will be summarized. Participant disposition including treatment group, analysis population, end of treatment study and reasons, end of study status and reason, and death date and reason will be listed.

Demographic data and baseline characteristics including age at informed consent, gender, race, ethnicity, time since most recent prior anti-PD-1 exposure, type of anti-PD-1 resistance and baseline LDH levels and vital signs (height, weight and ECOG status) will be summarized using descriptive statistics. Demographic data and baseline characteristics will be listed.

5.2. MEDICAL, MELANOMA AND BIOMARKER HISTORY

Medical history will be coded to system organ class (SOC) and preferred term (PT) using Medical Dictionary for Regulatory Activities (MedDRA) Version 24.0 and presented in a listing.

Melanoma history will be summarized by treatment group and overall, for the following variables. A separate listing will also be provided.

- Initial diagnosis stage
- Current disease stage with T, N, M
- Site(s) of metastatic disease

Initial diagnosis and current disease are collected for both pathological and clinical stages. If both are non-missing, then the pathological stage will be presented for summaries. Otherwise, the non-missing stage will be used.

Biomarker history will be summarized by treatment group and overall. Unless the mutation is specified below under the mutational analysis, the mutation will be grouped into the "Other, specify" category under each mutational analysis. A separate listing will also be provided.

- BRAF mutational analysis
 - o V600E
 - o V600K
 - o V600R
 - o V600D
 - o Other, specify
- NRAS mutational analysis
 - o NRAS Q61R
 - o NRASQ61K
 - o NRASO61L
 - o NRASO61H
 - NRASG12R
 - o NRASG12S
 - o NRASG12D
 - o NRASG12V
 - o NRASG13R
 - o NRASG13S
 - o Other, specify
- KIT mutational analysis
 - KIT L576P
 - o KIT K642E
 - o KIT V559A
 - o KITW557R
 - Other, specify
- Other, specify

5.3. CONCOMITANT MEDICATIONS

All medication verbatim terms collected will be coded to Anatomical Therapeutic Classification (ATC) and PT using the World Health Organization Drug Dictionary (WHO-DD) Version 24.0.

Concomitant medications will be summarized by presenting the number and percentage of participants by PT and ATC. Participants taking the same medication multiple times will only be counted once for that PT or ATC. Each summary will be ordered by descending order of incidence of ATC class and PT within each ATC class. Concomitant medications will be presented in a participant listing.

5.4. PRIOR SYSTEMIC AND INTRATUMORAL ANTI-CANCER THERAPY, PRIOR RADIOTHERAPY AND PRIOR/CONCOMITANT PROCEDURES

All verbatim terms collected of systemic and intratumoral anti-cancer therapy will be coded to ATC and PT using the WHO-DD Version March 2021 B3.

CONFIDENTIAL Page 25 19 November 2024

The prior systemic and intratumoral anti-cancer therapy will be summarized by presenting the number and percentage of participants by PT and ATC. Participants taking the same medication multiple times will only be counted once for that PT or ATC. Each summary will be ordered by descending order of incidence of ATC class and PT within each ATC class. If a participant experiences more than one prior systemic therapy, all unique therapies will be presented for the categorical summaries. In addition, the number of prior lines of therapy a patient received will be summarized. A participant will only be included in a single category once. All prior and subsequent systemic therapies will be presented in a participant listing.

The prior radiotherapy will be listed. The number and percentage of participants with prior radiotherapy will be summarized. If a participant experiences more than one prior radiotherapy, the total dose will be used for numerical summaries and the highest total dose delivered across the prior radiotherapies will be presented for categorical summaries. A participant will only be included in a single category once.

A listing of the number of prior systemic and intratumoral anti-cancer therapy and prior radiotherapy will be presented by each subject.

All prior procedures specific to melanoma will be summarized by SOC and PT as well as presented in a separate listing.

All concomitant procedures will be summarized by SOC and PT and will be presented in a separate listing. All concomitant procedures will be presented in a separate listing.

5.5. EXPOSURE AND STUDY DRUG COMPLIANCE

The number of participants who received lerapolturev and the total dose received will be summarized.

The following exposure variables will be summarized for lerapolturev:

- Number of cycles received
- Number of lesions injected
- Mean/median/Min, Max of TCID50 per cycle
- Mean/median/Min, Max of number of lesions per cycle
- Mean/median/Min, Max of sum of diameters (SOD) of injected lesions per cycle
- Mean/median/Min, Max of individual injected size (mm) per cycle
- Total TCID 50 received

The overall exposure to anti-PD-1 will be summarized and exposures to pembrolizumab and nivolumab will be summarized separately for the following variables:

- Number of cycles received
- Mean/median/Min, Max of dose received per cycle
- Mean/median/Min, Max of proportion of planned dose received (%)

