Statistical Methods	The primary endpoint for measuring anti-tumor activity will be ORR, based on RECIST 1.1, which will be summarized as the overall number (%) of participants with CR or PR in each treatment arm, along with 95% confidence interval (CI). Participants will be analyzed based on the treatment arm to which they were randomized, as well as by lerapolturev dose/schedule (ie, QW and Q3/4W). Other endpoints will be summarized by descriptive statistics, as appropriate. Further details for these and other analyses will be described in the statistical analysis plan (SAP).
Determination of Sample Size	Sample size was determined based on feasibility and logistical considerations. Based on an estimated sample size of 15 participants in Arm 2 receiving lerapolturev QW in combination with anti-PD-1, five objective responses are needed for the 95% confidence interval (CI) to be above 10% (33% ORR; 95% CI: 11.8% to 61.6%), which would indicate the combination has antitumor activity in this anti-PD-1 resistant population. See Section 8.3 for additional details regarding sample size determination.
Study Duration	Up to approximately 24 months (104 weeks)

Confidential Page 18 of 109

^Criteria for Crossover

- radiologic disease progression per RECIST v1.1 (progression does not need to be confirmed prior to crossover)
- has not had progression or confirmed partial response per RECIST v1.1 by week 26 on study
- partial response ≥ 6 months in duration

Confidential Page 19 of 109

Table 1. Schedule of Assessments for Lerapolturev Monotherapy or Lerapolturev + Pembrolizumab

NOTE: Cycle length for lerapolturev monotherapy or lerapolturev + pembrolizumab is 3 weeks. Lerapolturev is administered weekly during Cycles 1 & 2 and every 3 weeks thereafter on the days indicated in the table below. Refer to the table below for the timing of other study assessments to be completed within each cycle.

	Screening Period	o		EOT Visit ¹⁵	Survival Follow- up ¹⁶	
Study Procedure ³		Cycle 1	Cycle 2	≥ Cycle 3		
	(≤ 28D prior to C1D1)		+3W (+7D)	Q3W (+7D)	≤28D after last treatment	
Informed Consent ¹	X					
Medical History	X					
Physical Exam ^{2,3}	X	C1D1	C2D1	Day 1 of each Cycle	X	
Vital Signs ³	Х	C1D1, C1D8, C1D15	C2D1, C2D8, C2D15	Day 1 of each Cycle	X	
ECOG Performance Status ³	Х	C1D1	C2D1	Day 1 of each Cycle	Х	
PV Immunization Booster ¹	≥1W, but ≤6W before C1D1					
Adverse Events		Conti	Continuous from signing ICF until 30 days after last dose of study therapy			

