- **15. End of Treatment Visit** should be performed within 28 days after the last dose of study drug(s). The visit should include a focused and symptom-directed physical assessment, cutaneous, subcutaneous, and nodal tumor measurements (including photographs), as well as radiographic tumor imaging.
- 16. Survival Follow-up: Scans and cutaneous, subcutaneous and nodal lesion measurements performed per SOC should still be collected for participants in post-EOT survival follow-up who discontinued study treatments for reasons other than disease progression. The collection of lesion measurement (cutaneous, subcutaneous, and nodal, and scans) performed per SOC should continue until confirmed progression or the start of the next anti-cancer therapy. Sites should continue to collect post-study therapies and survival status for follow-up duration

Confidential Page 24 of 109

Table 2. Schedule of Assessments for Lerapolturev + Nivolumab

NOTE: Cycle length for lerapolturev + nivolumab is 4 weeks. Lerapolturev is administered weekly during Cycles 1 & 2 and every 4 weeks thereafter on the days indicated in the table below. Refer to the table below for the timing of other study assessments to be completed within each cycle.

	Screening Period	Treatment				Survival Follow- up ¹⁶	
Study Procedure ³		Cycle 1	Cycle 2	≥ Cycle 3			
	(≤ 28D prior to C1D1)		+4W (+7D)	Q4W (+7D)	≤28D after last treatment		
Informed Consent ¹	X						
Medical History	X						
Physical Exam ^{2,3}	X	C1D1	C2D1	Day 1 of each Cycle	X		
Vital Signs ³	x	C1D1, C1D8, C1D15 C1D22	C2D1, C2D8, C2D15	Day 1 of each Cycle	X		
ECOG Performance Status ³	X	C1D1	C2D1	Day 1 of each Cycle	Х		
PV Immunization Booster ¹	≥1W, but ≤6W before C1D1						
Adverse Events		Continuous from signing ICF until 30 days after last dose of study therapy					
Concomitant Medications		Continuous from signing ICF until 30 days after last dose of study therapy					
Subsequent Anticancer Therapy					Х	×	
AESI, irAEs and SAEs	Contin	Continuous from signing ICF until 90 days after last dose of study therapy or resolution/stabilization					
Hematology 3,4	X	C1D1	C2D1	C3D1 then Q8W (ie, at every other visit) and as clinically indicated	Х		
Chemistry ^{3,4}	Х	C1D1	C2D1	C3D1 then Q8W (ie, at every other visit) and as clinically indicated	Х		
INR, PT, PTT (or aPTT)	Х	As clinically indicated					
Thyroid Monitoring 3,5	X		Х	Day 1 of each Cycle	X		
Pregnancy Test ⁶	≤2D before C1D1			Q12W (±14D)			

Confidential Page 25 of 109

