5.7.1. Adverse Events

AE will be mapped to a MedDRA version 24.0 by SOC and PT. If a participant experiences multiple events that map to a single PT, the greatest severity and strongest assessment of relation to a study drug will be assigned to the PT for the appropriate summaries. AE severity will be assessed according to the NCI CTCAE version 5. If CTCAE grading does not exist for an AE, the severity of the AE will be graded as mild (1), moderate (2), severe (3), life-threatening (4), or death (5).

AESIs will be identified within the EDC by the investigator.

The number of participants for the following groups will be summarized by treatment group and overall:

- Any TEAE
- Any TEAE related to
 - o lerapolturev

- o anti-PD-1 therapy
- Any TESAE
- Any TESAE related to
 - o lerapolturev
 - o anti-PD-1 therapy
- Any treatment-emergent lerapolturev AESIs
- Any treatment-emergent irAEs
- Any TEAE with CTCAE grade ≥ 3
- Any TEAE related to
 - o lerapolturev with CTCAE grade ≥ 3
 - o anti-PD1 therapy with CTCAE grade ≥ 3
- Any Grade 5 TEAE
- Any Grade 5 TEAE related to lerapolturev or anti-PD1 therapy

The occurrence of TEAEs and TEAEs related to lerapolturev, or anti-PD-1 therapy will be summarized by PT, SOC, and severity. Additionally, TEAEs will be summarized by PT in descending frequency. All AEs reported will be listed for individual participants showing both verbatim and PT. All AEs that occurred prior to initiation of study drugs will be excluded from the tables but will be included in the listings.

Adverse events occurring during screening due to lerapolturev-related procedures that are not standard of care (eg, PV booster) will be considered related to lerapolturev and summarized separately.

Additional analysis may be conducted to investigate rates of TEAE based on lerapolturev dose and/or schedule. Should there be a difference, we may perform additional analyses to discern whether there is a relationship between dose and occurrence of AEs.

Missing onset dates will be imputed as previously outlined in Section 3.2.3.2 as required to determine TEAE.

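### SAP 5.5 summarises lerapolturev exposure per cycle, but on the weekly schedule a cycle holds 1, 3 or 4 injections, so identical dosing gives different figures

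*SAP*

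**What the plan says.** SAP 5.5 lists the lerapolturev exposure variables. Four use the cycle as their unit: "Mean/median/Min, Max of TCID50 per cycle", "Mean/median/Min, Max of number of lesions per cycle", and the corresponding rows for the sum of diameters of injected lesions and for individual injected size. The list also has "Number of cycles received" and "Total TCID 50 received". It has no row for dose per injection visit, for the number of injection visits, or for the share of the weekly series delivered. It does not say whether a per-cycle figure is an average over each participant's cycles or a display by cycle number.

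The schedules are in Protocol Tables 1 and 2, repeated as SAP Tables 2 and 3. The note to Protocol Table 1 (monotherapy or pembrolizumab, 3-week cycles) says: "Lerapolturev is administered weekly during Cycles 1 & 2 and every 3 weeks thereafter". The note to Protocol Table 2 (nivolumab, 4-week cycles) says: "Lerapolturev is administered weekly during Cycles 1 & 2 and every 4 weeks thereafter".

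Protocol 5.3 sets its limits per treatment visit: 3 ml, 1.6e9 TCID50 and 6 lesions.

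SAP section 5 displays the combination on the QW schedule as one group, with both anti-PD-1 drugs together. The split in SAP 5.5, "exposures to pembrolizumab and nivolumab will be summarized separately for the following variables", applies to anti-PD-1 exposure and not to lerapolturev.

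**The concern.** A per-cycle dose is readable when each cycle holds one injection visit, as in maintenance. In the weekly phase it mixes the dose given at a visit with the number of visits that fall inside the cycle, and that number depends on the cycle number and on the partner drug.

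Two participants with the same injections on the same days can therefore show different exposure. The pooled Arm 2 QW figure moves with the mix of pembrolizumab and nivolumab, so it is not comparable with Arm 1, where everyone is on 3-week cycles. A per-cycle figure also cannot be read against limits that the protocol sets per visit.

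The crossover groups add to the mixing. Under Protocol 3.1.1 some participants continue their schedule on crossover and others receive the seven weekly injections again.

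What is at stake is the account of the amended regimen. The weekly series of seven is the main dosing change in Amendment 4, and the efficacy hypothesis in Protocol 8.2 concerns that schedule. The section heading includes compliance, yet nothing planned for lerapolturev shows how much of the series was given.

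**Working it through.** **Inputs.** Maximum volume 3 ml per visit and concentration 5.33e8 TCID50/ml (Protocol 5.3). Injection days from Protocol Tables 1 and 2. All figures assume a constant dose at the visit maximum and every scheduled injection given on its planned day. The ratios are the same at any other constant dose per visit.

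**1. The plan's own figures.** 3 × 5.33e8 = 1.599e9, which rounds to the stated 1.6e9. Weekly injections: monotherapy/pembrolizumab 3 (Cycle 1) + 3 (Cycle 2) + 1 (Cycle 3 Day 1) = 7; nivolumab 4 + 3 = 7. Both agree with the stated seven, and in both the seventh falls on Day 43.

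**2. Same seven injections, averaged over cycles started.** The total is 7 × 1.6e9 = 11.2e9 in both.
- Monotherapy/pembrolizumab, 3 cycles started: 11.2e9 / 3 = 3.73e9.
- Nivolumab, 2 cycles started: 11.2e9 / 2 = 5.60e9.
- Ratio: 5.60 / 3.73 = 1.5.

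The documents do not give the share of Arm 2 on nivolumab. At this point the pooled figure could lie anywhere from 3.73e9 (none) to 5.60e9 (all) with no difference in dosing.

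**3. Same schedule, shown by cycle number.**
- Cycle 1: 3 × 1.6e9 = 4.8e9 against 4 × 1.6e9 = 6.4e9, ratio 1.33.
- Cycle 2: 4.8e9 in both.
- Cycle 3 onward: 1.6e9 in both.

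**4. Participant average by number of completed cycles** = cumulative injections × 1.6e9 / cycles.

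| Cycles | Mono/pembro injections | Mono/pembro per cycle | Nivolumab injections | Nivolumab per cycle |
|---|---|---|---|---|
| 2 | 6 | 4.80e9 | 7 | 5.60e9 |
| 4 | 8 | 3.20e9 | 9 | 3.60e9 |
| 8 | 12 | 2.40e9 | 13 | 2.60e9 |
| 12 | 16 | 2.13e9 | 17 | 2.27e9 |

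On monotherapy/pembrolizumab the average falls 4.80 / 2.13 = 2.25-fold between 2 and 12 cycles at an unchanged dose per visit. Stopping after one injection gives 1.6e9, the lowest possible value at this dose. Stopping after two gives 3.2e9.

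**5. The total row, for contrast.** On monotherapy/pembrolizumab it is 6 × 1.6e9 = 9.6e9 after 2 cycles and 12 × 1.6e9 = 19.2e9 after 8. It is equal for equal dosing and rises with time on treatment.

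**6. Lesion counts.** If lesions are counted at each injection, an induction cycle can show up to 3 × 6 = 18 lesions, or 4 × 6 = 24 in nivolumab Cycle 1, against a visit limit of 6. The SAP does not say whether lesions within a cycle are counted once.

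**7. Per injection visit.** Every participant in steps 2 to 5 shows 1.6e9, whatever the partner drug or time of stopping.

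**The case against.** The best defence is that exposure is not summarised by cycle alone. Total TCID50 is planned, does not depend on how cycles are cut, and is lowest for those who stop early. That stands, and it limits the harm. It does not remove it, because a total cannot separate a lower dose per visit from fewer visits, and it does not show how much of the weekly series was given.

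The 1.5-fold gap is also a snapshot, taken when Cycle 3 has just begun on the 3-week schedule. Over two completed cycles the gap is 5.60 / 4.80, or 17%, and part of it is real because nivolumab participants have then had one more injection. At 12 cycles it is 2.27 / 2.13, about 6%. That stands too: the distortion is largest early and fades.

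Four stronger readings are tempting, and the documents do not support them.
- A reader might infer that early stoppers will always appear to have the highest dose. This needs averaging within participant, which the SAP does not state, and it fails for anyone who stops after one or very few injections.
- A reader might extend the fault to anti-PD-1. Protocol 5.3 speaks of each drug's own cycle, so dose per cycle can mean dose per administration. SAP 5.5 already separates the two drugs and reports the proportion of planned dose received.
- A reader might apply it to all four per-cycle rows alike. The mean size of individual injected lesions barely depends on how many injections a cycle holds.
- A reader might expect the fault to carry into the adverse-event analysis. SAP 5.7.1 says only that "we may perform additional analyses to discern whether there is a relationship between dose and occurrence of AEs", and it names no dose measure.

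**Conclusion.** The point holds for TCID50, number of lesions and sum of diameters. The per-cycle unit varies with cycle number and partner drug, and Arm 2 on the QW schedule pools the drugs, so identical dosing yields different exposure figures. The partner-drug difference appears on either reading of the SAP wording: 1.5-fold at Day 43 if averaged over cycles started, or 1.33-fold in Cycle 1 if shown by cycle number. The fall with time on treatment after induction arises only if the figure is averaged within participant.

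These sizes rest on a constant dose per visit and full adherence to the planned days. Real doses vary with lesion size, so the observed differences will be some mixture of this artefact and true variation, which the planned table cannot separate.

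The effect is confined to a descriptive exposure table. ORR, its confidence interval and the sample size reasoning are not affected, and the point says nothing about whether the dosing schedule is right. It is worth correcting because the correction is simple and concerns the main change to the regimen.

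**What to change.** In SAP 5.5 and Table 14.1.5.1:
- Report TCID50, lesions injected and sum of diameters of injected lesions per injection visit.
- Add the number of injection visits received.
- For participants who start the weekly series of seven, add the number and percentage of the seven received, counted from the start of that series. For those who cross over mid-series, combine monotherapy and combination injections. Show a repeat series separately.
- Keep total TCID50.
- Show any per-cycle row that is retained by cycle number and by partner drug.

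The anti-PD-1 rows need no change. A cumulative dose to a fixed day such as Day 43 is not advised: the schedules allow cycles to start up to 7 days late, so a seventh injection given within the window could be missed.

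The cost is revised SAP wording, a few extra table rows and some reprogramming. The injection data are already planned for Listing 16.2.5.1, and no dosing rule changes.

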5.6. EFFICACY

5.6.1. Primary Efficacy Endpoints

The primary efficacy endpoint is ORR which is the overall number and percentage of participants in each treatment arm with confirmed CR or confirmed PR. The primary analysis for the safety run-in and Arm 1 will include participant response prior to crossover to Arm 2. ORR will be analyzed by treatment arm, dosing schedule and overall.

CONFIDENTIAL Page 26 19 November 2024

